## 10. STUDY TREATMENT

### 10.1. Investigational Study Medication

The study medications for the study are A-101 45%, and matching Vehicle. All study medications are clear, colorless solutions which are indistinguishable in physical appearance.

**Table 3: Study Medication Information**

| Study Medication Name      | A-101 45%  | Vehicle |
|----------------------------|--|---------|
| Manufacturer               | James Alexander Corporation, Blairstown NJ   |         |
| A-101 concentration (%)    | 45   | 0       |
| Pharmaceutical Form        | Solution   |         |
| Storage Conditions         | 59°F to 77°F (15°C to 25°C) excessive heat, open flame and combustibles, out of direct sunlight and in a well-ventilated, dry area   |         |
| Route                      | Topical  |         |
| Frequency                  | A-101 Study Medication will be applied twice a week for 8 weeks.   |         |
| Duration of Administration | Apply study medication to each identified common wart for approximately 15 seconds. Allow each treated wart to remain undisturbed for approximately 15 seconds. Repeat the application/waiting cycle until the study medication has been applied to each identified common wart up to 3 times. |         |
| Activated Applicators      | Activated applicators are stable for 4 hours at room temperature (59°F to 77°F or 15°C to 25°C)  |         |

### 10.2. Subject Randomization

Prior to the start of the study, Aclaris Therapeutics, Inc./designee will generate a randomization list that will be provided to the assigned clinical packaging organization for study medication labeling.

The randomization list will be stored with limited access to designated personnel for study medication labeling.

Aclaris Therapeutics, Inc.

Protocol Number: A-101-WART-302

Amendment 3: Version 5 14 February 2019

Subjects will be randomized to the study in a 1:1 ratio and stratified by investigational study site. Sites will be shipped study medication in blocks of 4. Once a subject is determined to have met all inclusion criteria and does not meet any of the exclusion criteria, the site will pull the next sequential drug kit from their supply and enter the drug kit number into the EDC system.

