**Number of Patients to be Enrolled:**

Approximately 500 subjects will be randomized to the study.

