**Number of Study Sites:**

This study will be conducted in the US only at approximately 25 treatment centers.

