A-101 ( $H_2O_2$ ) 45% (w/w) Topical Solution administered once weekly and twice weekly was well tolerated. Treatment emergent adverse events were predominantly mild and unrelated to study medication. Local Skin Reactions (LSRs) were predominantly mild and transient. The LSRs of pruritus and stinging reported by subjects, and crusting, edema, erythema, and scaling reported by the investigator following treatment generally resolved by Visit 13 (Day 134). There were no clinically significant changes during the study in laboratory evaluations or vital signs.

Aclaris Therapeutics, Inc.

Protocol Number: A-101-WART-302

Amendment 3: Version 5 14 February 2019

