### 7.2. Duration of Study

The anticipated time for study enrollment is approximately 3 months. The duration of study participation is anticipated to be a maximum of 157 days per subject. Subjects will have a total of 13 study visits. The maximum anticipated duration for the study is approximately 10 months.

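### Protocol 10.2 tells sites the block size (4, sequential kits, by site), so a site that recognises earlier allocations could foresee some later ones at enrolment

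*Protocol*

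**What the plan says.** Protocol 10.2 gives everything needed to work out the allocation structure at a site:

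- Ratio and stratification: "Subjects will be randomized to the study in a 1:1 ratio and stratified by investigational study site".
- Block: "Sites will be shipped study medication in blocks of 4".
- Order of use: "the site will pull the next sequential drug kit from their supply and enter the drug kit number into the EDC system".

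Neither the protocol nor the SAP mentions another block size or any variation in it. The stated protections are restricted access to the randomization list (Protocol 10.2) and matching appearance of the two solutions (Protocol 10.1). Neither hides the block size.

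On cues, Protocol 5.2 lists Phase 2 reactions that include "crusting, edema, erythema, and scaling reported by the investigator following treatment", and calls them mostly mild and short-lived. Protocol 10.7 provides for severe erythema and edema during an application. Protocol 12.4 warns of bleached clothing. In-office applications are watched by the physician or trained staff (Protocol 10.5), and subjects are observed for at least 20 minutes afterwards (Protocol 14.2.1).

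On scale, the synopsis says "Approximately 500 subjects will be randomized to the study" and "This study will be conducted in the US only at approximately 25 treatment centers". Protocol 7.2 says "The anticipated time for study enrollment is approximately 3 months".

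**The concern.** Matching solutions conceal an allocation only until something reveals it. With a known 2:2 block used in order, each recognised allocation narrows what is left. Once two subjects in a block are known to have had the same arm, the rest of that block is known too.

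What is at stake is selection. Eligibility is re-assessed at Visit 2 just before the kit is pulled (Table 2, notes 1 and 12). Several criteria rest on investigator opinion: clinical significance of laboratory values, general health, interfering conditions, and likelihood of completing (Protocol 8.1 and 8.2). An investigator who expects a particular arm could, even without intent, reconfirm, defer or exclude a subject differently. The primary CMH test stratifies by number of warts. That does not correct for which subjects were let in.

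**Working it through.** The documents give no predictability figure, so there is none to reproduce.

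**Inputs.** Block 4, ratio 1:1, sequential use (Protocol 10.2). About 500 subjects, 25 centers and 3 months (synopsis; Protocol 7.2). This gives 500/25 = 20 subjects and 20/4 = 5 blocks per site. With 3 months taken as 90 days and even enrolment, there is one subject per site every 90/20 = 4.5 days. Recognition rates are not in the documents and are assumed below.

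**Step 1: ceiling, every earlier allocation recognised at once.** There are 6 equally likely orders of two active and two vehicle.

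| Position | P(certain) | P(best guess right) |
|---|---|---|
| 1 | 0 | 1/2 |
| 2 | 0 | 2/3 |
| 3 | 1/3 | 1/3 × 1 + 2/3 × 1/2 = 2/3 |
| 4 | 1 | 1 |
| Mean | (4/3)/4 = 33.3% | (17/6)/4 = 17/24 = 70.8% |

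One third of 500 is about 167 allocations, or 20/3 = 6.7 at an average site.

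**Step 2: perfect but delayed recognition.**

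- Latest subject not yet seen: (1/2 + 1/2 + 2/3 + 2/3)/4 = 7/12 = 58.3% right, and (1/3)/4 = 8.3% certain.
- Latest two not yet seen: (1/2 + 1/2 + 1/2 + 2/3)/4 = 13/24 = 54.2% right, and none certain.

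Delay is realistic if recognition waits for the next visit. From Day 1 to Day 8 is 7 days, and 7/4.5 = 1.6 further subjects enrol at an average site. Recognition during the application or the 20-minute observation would avoid the delay.

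**Step 3: imperfect recognition, no delay.** Bayes best guess over the 6 orders. The pair is the chance of being seen as active when on active / when on vehicle.

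| Assumed pair | Best guess right |
|---|---|
| 0.90 / 0.05 | 66.4% |
| 0.80 / 0.10 | 62.6% |
| 0.50 / 0.10 | 56.5% |

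At 0.50/0.10 with two subjects unseen it is 51.7%, close to chance.

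**Step 4: other block schemes, full and immediate recognition.** For varied blocks, sizes are equally likely, there are 20 subjects per site, and the observer knows which sizes may occur but not their order.

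| Scheme | Certain | Best guess right |
|---|---|---|
| Fixed 4 (current) | 33.3% | 70.8% |
| Fixed 6, known | 25.0% | 68.3% |
| Fixed 8, known | 20.0% | 66.6% |
| Varied 2, 4, 6 | about 4% | about 70% |
| Varied 4, 6, 8 | about 2% | about 67% |

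Varying the block removes nearly all certainty. It barely lowers guessing accuracy, because guessing the arm used less often so far needs no knowledge of block size.

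**The case against.** The strongest reply is that 33% and 71% need perfect recognition before the next kit is pulled, and nothing in the documents shows it. No reaction rates by arm are given, and Phase 2 reactions were mostly mild. Both arms are rubbed firmly with alcohol before treatment (Protocol 10.7), so some redness need not point to active. Formal skin-reaction grading comes before each application (Protocol 13.1), so the Visit 2 grade is a baseline. All of this stands, and it is why the figures are a ceiling with a range beneath it.

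Warts are also chosen at Visit 1, up to about two weeks before randomization, against size and grade criteria (Protocol 12.1), which limits the room for selection. That stands too. What remains is discretion over timing and over the Visit 2 reconfirmation.

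A reader might infer that block predictability biases the PWA rating. The documents do not support that link. A rater who guesses the arm from a subject's own reactions can do so at any block size, and changing the blocks would not help. A reader might also infer that allocations were in fact foreseen. Nothing in either document shows this.

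Finally, Protocol 10.2 speaks of how medication is shipped. That the randomization block is also 4 and constant is the natural reading, but it is not stated.

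**Conclusion.** The point holds as a conditional, moderate weakness in allocation concealment. Protocol 10.2 gives sites a single block size that they do not need in order to use kits in sequence.

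Its size depends on recognition. The ceiling is 33% of allocations certain and 71% of guesses right. Under the assumed recognition rates the share of right guesses is 66% to 57%, and with delayed but perfect recognition 58% or 54%. Combined delay and weak recognition bring it close to 50%.

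This rests on three assumptions: the randomization block equals the shipping block, sites enrol about 20 subjects each at an even pace, and active treatment gives cues that vehicle does not. The exposure is to selection at enrolment only.

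**What to change.** 1. Delete the block size from Protocol 10.2 and keep it in a randomization specification closed to sites. Ship kits in quantities that do not mark where blocks begin.
2. For any list or kits not yet released, use randomly varied, undisclosed block sizes, preferably without blocks of 2 (for example 4, 6 and 8). A block of 2 always gives away its second allocation once the first is known.

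Under full recognition, certain allocations at a 20-subject site fall from 6.7 to about 0.4 (2% of 20). Best-guess accuracy moves only from 71% to about 67%, so the change should not be presented as restoring chance-level guessing.

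The cost is a new list and new labels for unreleased kits, and slightly more treatment imbalance within sites. Simply lengthening a disclosed block would not be enough: a known block of 6 still leaves 25% certain.

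There is no benefit for kits already used, and sites already know the block size behind them. SAP 3.6 records a correction made after unblinding, so for this trial the change may come too late. It would then apply to later studies that use the same kit system.

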### **10.3. Study medication packaging, storage, and dispensing**

A-101 45% and matching Vehicle will be provided by Aclaris Therapeutics, Inc. and labeled according to applicable regulatory requirements.

The study medication will be packaged in single use applicators. The ampoule is provided inside a sealed polyethylene tube with a flocked, doe foot applicator on one end.

Subject kits will contain 20 study medication applicators. The blinded subject kits will remain at the investigational site and the site staff will dispense a study medication applicator to the subject for the at home treatment visit. The outside of each subject kit and each individual treatment applicator will be labelled in compliance with applicable regulatory requirements.

A-101 study medication must be stored in a location where there is limited access at 59°F to 77°F (15°C to 25°C) protected from excessive heat, open flame and combustibles, out of direct sunlight and in a well-ventilated, dry area. Proper storage of the A-101 study medication must be reviewed with the subject prior to dispensing the blinded subject kit.

Investigational study medication supplies are only to be used for subjects properly consented and randomized to this study.

### **10.4. Drug Accountability**

The investigator or designee will maintain an accurate record of the receipt of the study medications as shipped by Aclaris Therapeutics, Inc. (or designee), including the date received and the condition of the study medications. One copy of this receipt will be returned to Aclaris Therapeutics, Inc. (or designee) when the contents of the study medication shipment have been verified and one copy maintained in the study file. In addition, an accurate study medication disposition record will be kept, specifying the amount dispensed for each subject and the date of dispensing. This inventory record will be available for inspection at any time. At the completion of the study, the original inventory record will be available for review by Aclaris Therapeutics, Inc. upon request.

Final drug accountability will be completed by the CRA at the completion of the study and all unused study medication will be returned to Aclaris Therapeutics, Inc. drug depot for disposal per Aclaris Therapeutics, Inc. (or designee's) written instructions.

### **10.5. Study Medication Treatment**

The study medications are for external, topical use only and are to be applied only to those subjects that have been properly consented and randomized to the study.

The investigational center staff member must comply with the study medication storage conditions outlined in Section [10.1](#)

During Visit 2-Visit 9 (if the identified common wart meets the criteria for retreatment), the investigational study staff will select the appropriate study medication applicator for treatment of a specific subject. Subjects ages 18 years of age and older will apply the appropriately labeled A-101 study medication to the identified common wart in the presence of the treating investigator or investigational staff that has been trained on the protocol. The second weekly application of the A-101 study medication will be applied by the subject at home (Days 4, 11, 18, 25, 32, 39, 46, and 53). The second weekly treatment will be determined by the PWA assessment performed during the in-office visit. If the identified common wart meets the criteria for retreatment, then the subject will apply the A-101 study medication at home.

Subjects between the ages of 1 and 17 years of age will have their A-101 study medication applied in the office by a parent or legal guardian in the presence of the treating physician or a member of the investigational site staff during Visit 2-Visit 9. The second weekly A-101 study medication application will be applied at home by a parent or a legal guardian (Days 4, 11, 18, 25, 32, 39, 46, and 53). The second weekly treatment will be determined by the PWA assessment performed during the in-office visit. If the wart meets the criteria for retreatment, then the subject will apply the A-101 study medication at home.

**Retreatment Criteria:**

At Visit 3-9, if the identified common wart has a **PWA grade of >0** then the subject will receive re-treatment with the A-101 study medication treatment. However, treatment with the A-101 study medication should not be applied if any of the following criteria apply to the identified common wart:

- The common wart has a pre-treatment LSR grade of 3 (severe) for any sign or symptom AND the grade has increased compared to the previous visit.
- The common wart is, in the investigator's opinion, not appropriate for a retreatment (the investigator must note the reason on the subject's Comments CRF page).
- The common wart, in the Investigator's opinion, cannot be visualized so the Investigator cannot assess the PWA.

If the identified common wart meets the criteria for re-treatment during the in-office visit (PWA>0), then the subject/parent/legal guardian should treat the common wart at home on the protocol defined at home treatment days (Days 4, 11, 18, 25, 32, 39, 46, 53. A window of +1 day is allowed). If the subject is unable to tolerate treatment the day of an at home treatment visit due to severe skin irritation, then the treatment should be held and the investigational site should be notified.

Subjects whose identified common wart(s) is assessed at a particular visit (V3-V9) to be a PWA=0 will not have the that common wart re-treated at that visit (or retreated at the second at home application that week).

[figure not shown]

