The investigator and subject will assess each identified common wart for local skin reactions associated with irritation at Visits 2-13. At Visit 2-Visit 9, the investigator and subject will assess each identified common wart for LSRs prior to the application of the study medication. Refer to Section [13.1](#) for the complete list of Local Skin Reaction signs and symptoms.

During in-office visits, subjects 18 years of age and older will apply their A-101 study medication in the presence of the treating physician or a member of the investigational study staff that has been trained on the protocol. Subjects ages 1 to 17 will have their A-101 study medication applied by a parent/legal guardian in front of the treating physician or a member of the investigational study staff during in-office visits. If the identified common wart meets the criteria

for re-treatment as defined in Section 10.6 the lesion will be re-treated at Visits 3-9. Following application of study medication, subjects must NOT wash/submerge the treated wart for at least 6 hours and they must NOT apply any topical products to the treated common warts for at least 6 hours. Parents/legal guardians of children must ensure that the child does not put the treated area in their mouth, or eyes, until completely dry after the application. If the treated area is not completely dry 10 minutes after the application, the area should be blotted dry.All subjects will receive their second weekly treatment of the A-101 study medication at home on Days 4, 11, 18, 25, 25, 32, 39, 46, 53 as determined by the PWA assessment performed during the in-office visit. Subjects ages 1 to 17 will have their A-101 study medication applied by a parent or legal guardian. All subjects will need to document the application of A-101 study medication in a subject diary. The second weekly treatment will depend on the PWA performed during the in-office visit that week. If the identified common wart meets the criteria for re-treatment during the in-office visit, then the subject/parent/guardian will perform the second weekly treatment at home.

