### **12.3. Physician's Wart Assessment (PWA)**

The Physician's Wart Assessment (PWA) is the Investigator's assessment of the severity of each identified common wart at a particular time point. The Investigator should NOT refer to any other assessments to assist with this evaluation. This evaluation IS NOT a comparison with the PWA performed at any other visit.

At every study visit, the Investigator will assess each identified common wart and report the one integer that best describes the common wart severity using the following scale. At any visit where a study medication treatment is performed, the PWA must be completed prior to the treatment visit.

| Physician's Wart Assessment |   |
|------------------------------------|---|
| Grade                       | Descriptor   |
| 0                           | Clear: No visible wart. No further treatment is indicated                         |
| 1                           | Near Clear: a visible wart that is less than 3 mm in maximal diameter (or length) |
| 2                           | A visible wart $\geq$ 3 mm and $<$ 6 mm in maximal diameter (or length)           |
| 3                           | A visible wart $\geq$ 6 mm in maximal diameter (or length)                        |

The physician is encouraged to use a ruler or caliper and to feel the wart or skin area to help his/her assessment.

At Visit 1 for the subject to be enrolled and at Visit 2 for the subject to be randomized each identified wart must have a PWA grade  $\geq$  2.

At Visits 3-9, identified common warts must have a PWA  $> 0$  to be retreated. If the Investigator cannot assess the PWA for a common wart (e.g., the common wart cannot be visualized because of an LSR such as edema, scabbing, etc.) she/he must report the reason in the subject's CRFs. The identified common wart must not be retreated at that visit, and the subject should be seen at the next scheduled visit. All at home treatment visits will be based on the PWA score during the in-office visit.

Refer to [Appendix 2](#) for the PWA Site Manual.

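### The protocol conflicts with itself on whether an office hold for a newly severe skin reaction, or on investigator judgement, also covers that week's home application

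*Protocol*

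**What the plan says.** Under Retreatment Criteria in protocol Section 10.5, a wart with PWA above 0 at Visits 3 to 9 is to be re-treated. That is then qualified: "treatment with the A-101 study medication should not be applied if any of the following criteria apply to the identified common wart". Three conditions follow. The first is a "pre-treatment LSR grade of 3 (severe) for any sign or symptom AND the grade has increased compared to the previous visit". The second is that the investigator judges the wart unsuitable for re-treatment. The third is that the wart cannot be seen well enough to grade.

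The home application is described in several places:

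- Section 10.5, Retreatment Criteria: "If the identified common wart meets the criteria for re-treatment during the in-office visit (PWA>0), then the subject/parent/legal guardian should treat the common wart" on the scheduled home day.
- Section 10.5, main text, once for adults and once for ages 1 to 17: one sentence says the office PWA determines the second weekly treatment. The next makes it depend on the re-treatment criteria, without the PWA bracket.
- Table 2, footnote 15 (repeated in the SAP schedule of assessments): "The second weekly treatment will depend on the PWA performed during the in-office visit that week". The following sentence again refers to the re-treatment criteria, without the bracket.
- Section 12.3: "All at home treatment visits will be based on the PWA score during the in-office visit".

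One decision not to treat is expressly extended to the home application. A wart graded PWA 0 "will not have the that common wart re-treated at that visit (or retreated at the second at home application that week"). No such sentence exists for the LSR hold or the investigator-judgement hold.

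Section 10.5 also has a home-day rule: if the subject cannot tolerate treatment that day because of severe skin irritation, the application is held and the site is told. SAP Section 3.3.1 computes compliance from office re-treatment and home diary records, and subtracts warts with PWA 0 or an LSR of grade 3 at the latest assessment.

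**The concern.** A wart held for a newly severe reaction, or on the investigator's judgement, will often still be visible, so its PWA will still be above 0. If the home rule is read as a PWA rule, that wart qualifies for an application of 45% hydrogen peroxide (in the active arm) by the subject or a parent, before anyone at the site has graded it again. If it is read as the full re-treatment criteria, the same wart is left alone until the next visit.

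Two things are at stake. The first is safety: the wart could be re-exposed outside the clinic after a deliberate decision not to treat, in a trial that enrols children from 1 year of age. The second is consistency: sites that read the rule differently would deliver different exposure for the same reaction, and the compliance figure would not reveal which rule was followed.

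**Working it through.** **Schedule.** Inputs are the visit days in protocol Section 7 and the windows in Table 2.

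- Office treatment days: 1, 8, 15, 22, 29, 36, 43, 50 (8 days). Home days: 4, 11, 18, 25, 32, 39, 46, 53 (8 days). Total 8 + 8 = 16, which reproduces the plan's maximum of 16 applications.
- Nominal gap = home day minus office day: 4 − 1 = 3, 11 − 8 = 3, and so on to 53 − 50 = 3. It is 3 days every week.
- With windows (office ±1 day at Visits 3 to 9, home +1 day), taking Visit 3 as the example: shortest 11 − (8 + 1) = 2 days, longest (11 + 1) − (8 − 1) = 5 days. The other weeks give the same range.
- The re-treatment decision is made at Visits 3 to 9, which is 7 visits. The home days that follow are 11, 18, 25, 32, 39, 46 and 53, so 7 of the 8 home applications are affected. Day 4 follows the first treatment at Visit 2.

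**Text side by side.**

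| Place | Points to PWA only | Points to full criteria, holds included |
|---|---|---|
| 10.5, Retreatment Criteria | PWA bracket in the home sentence; carry-over written for PWA 0 only | The condition is framed as meeting the re-treatment criteria, under the heading that lists the holds |
| 10.5, main text | PWA determines the home treatment | Next sentence: re-treatment criteria, no bracket |
| Table 2 footnote 15; same footnote in SAP | Depends on the office PWA | Next sentence: re-treatment criteria, no bracket |
| 12.3 | Based on the PWA score | None |
| SAP 3.3.1 | None | LSR grade 3 warts subtracted from a count that includes home records |

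**Worked case.** A wart has PWA 2 at Visit 4 (Day 15), and an LSR sign has gone from grade 1 at Visit 3 to grade 3. The office hold applies. On the left-hand column the wart is due at home on Day 18. On the right-hand column it is not. Each answer can be defended from the protocol.

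**Can a site settle it by cross-reference?** Not from Table 2. Footnote 14 sends the reader to Section 10.6 for the re-treatment criteria, but that section covers preparing the applicator. The criteria are in Section 10.5.

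**Compliance rule against the protocol hold.** The protocol's LSR hold needs grade 3 and an increase. The SAP subtracts on grade 3 alone. A wart that stays at grade 3 without increasing is not caught by the protocol's LSR hold, yet the SAP subtracts it. A wart held on investigator judgement with LSRs below grade 3 and PWA above 0 is withheld under the protocol, yet the SAP does not subtract it.

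**The case against.** The strongest reply is that no passage tells anyone to treat a held wart at home. The holds are listed under the re-treatment criteria and are not worded as limited to the office application, so a held wart can fairly be read as not meeting those criteria. The SAP compliance rule leans the same way. This stands. A reader might infer that the home application depends on the PWA alone, so that a held wart is necessarily sent for home treatment. The documents do not support that. They support two readings.

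There are also safeguards. The home-day hold covers severe irritation the subject cannot tolerate. Section 10.3 keeps kits at the site, with staff dispensing the home applicator. Both help, but neither closes the gap. The first rests on the subject's or parent's view on the day, not on the investigator's grading. The second is weak when the subject has other eligible warts (up to 6 are allowed) and takes an applicator home anyway.

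Three further inferences are tempting and should not be drawn:

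- That severe reactions are to be expected in the active arm. Section 5.2 describes Phase 2 LSRs as predominantly mild and transient.
- That the office and home severity thresholds contradict each other. One is an investigator's graded LSR, the other a subject's tolerance on the day. Assessor and setting differ.
- That a wart which cannot be visualised is sent home for treatment. Without a PWA score, a PWA above 0 is not met even on the narrow reading.

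**Conclusion.** The conflict is real but narrower than an instruction to re-treat held warts. For the LSR hold and the investigator-judgement hold, the protocol gives two incompatible answers on that week's home application. Section 12.3 read literally gives one; the re-treatment-criteria wording in Section 10.5 and footnote 15 allows the other. The ambiguity can arise at 7 of the 8 home applications, nominally 3 days after the hold and 2 to 5 days with windows.

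How many subjects would meet it is unknown, because neither document gives a rate of newly severe LSRs or of judgement holds. The conclusion rests only on the wording and on a held wart still having PWA above 0. A figure after the criteria in Section 10.5 and one in the subject instruction sheet are not shown, so nothing is inferred from either.

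This should be corrected because it concerns unsupervised re-exposure and consistency of delivered treatment. It does not undermine the primary analysis, and the existing safeguards reduce its weight.

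**What to change.** Reconcile protocol Section 10.5 (main text and Retreatment Criteria), Section 12.3, Table 2 footnote 15 and the matching SAP footnote so that one rule decides the home application:

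1. Replace the PWA-only wording with a cross-reference to the full re-treatment criteria in Section 10.5, and correct footnote 14, which now points to Section 10.6.
2. State for each office hold whether it covers that week's home application, wart by wart, as is already done for PWA 0.
3. Align the SAP Section 3.3.1 compliance rule with the protocol's hold wording. At present one uses grade 3 and the other uses grade 3 with an increase.

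Which rule stands is for the sponsor's clinical team, and none is proposed here. The cost is wording changes in the protocol and SAP plus a memo to sites, with no added visits, assessments or subjects.
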